16.3 REPEATED OR UNSCHEDULED ASSESSMENTS OF SAFETY PARAMETERS

If a patient has repeated assessments before the start of OLTP, the results from the final nonmissing assessment made before the start of the OL IP will be used as baseline. If end-of-study assessments are repeated or if unscheduled visits occur, the last nonmissing postbaseline assessment will be used as the end-of-study assessment for generating summary statistics. However, all postbaseline assessments will be used for PCS value determinations, and all assessments will be presented in the data listings.

16.4 MISSING DATE OF THE LAST DOSE OF INVESTIGATIONAL PRODUCT

When the date of the last dose of OL IP is missing for a patient in the OL Safety Population, all efforts should be made to obtain the date from the Investigator. If after all efforts are made it is still missing, the last visit date during the corresponding period will be used as the last dose date for the corresponding period.

When the date of the last dose of DB IP is missing for a patient in the DB Safety Population, all efforts should be made to obtain the date from the Investigator. If after all efforts are made it is still missing, the last visit date will be used as the last dose date.

16.5 MISSING SEVERITY ASSESSMENT FOR ADVERSE EVENTS

If severity is missing for an AE that started before the date of the first dose of OL IP, an intensity of mild will be assigned. If severity is missing for an AE that started on or after the date of the first dose of OL IP, an intensity of severe will be assigned. The imputed values for severity assessment will be used for the incidence summary; the values will be shown as missing in the data listings.

16.6 MISSING CAUSAL RELATIONSHIP TO INVESTIGATIONAL PRODUCT FOR ADVERSE EVENTS

If the causal relationship to the IP is missing for an AE that started on or after the date of the first dose of OL IP, a causality of yes will be assigned. The imputed values for causal relationship to OL or DB treatment will be used for the incidence summary; the values will be shown as missing in the data listings.

16.7 MISSING DATE INFORMATION FOR ADVERSE EVENTS

The following imputation rules only apply to cases in which the start date for Aes is incomplete (ie, partly missing).

Missing month and day

- If the year of the incomplete start date is the same as the year of the first dose of OL IP, the month and day of the first dose of OL IP will be assigned to the missing fields
- If the year of the incomplete start date is before the year of the first dose of OL IP, *December 31* will be assigned to the missing fields
- If the year of the incomplete start date is after the year of the first dose of OL IP, *January 1* will be assigned to the missing fields

Missing month only

- If only the month is missing, the day will be treated as missing and both the month and the day will be replaced according to the above procedure

Missing day only

- If the month and year of the incomplete start date are the same as the month and year of the first dose of OL IP, the day of the first dose of OL IP will be assigned to the missing day
- If either the year of the incomplete start date is before the year of the date of the first dose of OL IP or if both years are the same but the month of the incomplete start date is before the month of the date of the first dose of OL IP, the last day of the month will be assigned to the missing day

- If either the year of the incomplete start date is after the year of the date of the first dose of OL IP or if both years are the same but the month of the incomplete start date is after the month of the date of the first dose of OL IP, the first day of the month will be assigned to the missing day

If the stop date is complete and the imputed start date as above is after the stop date, the start date will be imputed by the stop date.

If the start date is completely missing and the stop date is complete, the following algorithm will be used to impute the start date:

- If the stop date is after the date of the first dose of OL IP, the date of the first dose of OL IP will be assigned to the missing start date
- If the stop date is before the date of the first dose of OL IP, the stop date will be assigned to the missing start date

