7.0 STUDY PATIENTS

7.1 PATIENT DISPOSITION

The OLTP starts with the first dose of OLTP and ends with one of the following: the last scheduled assessment at Visit 12 (Week 16) or early termination (ET) before Visit 12 for patients who do not enter the DBTP; or 1 day before the date of the first dose of DBTP (or the date of the first dose of the DB IP if the last scheduled assessment date in the OLTP is on the date of the first dose of the DBTP) for patients who enter the DBTP.

The DBTP starts with the first day of randomization and ends with the last scheduled assessment at Visit 31 (Week 55) or ET.

The SFU period starts one day after the end of the previous period and ends with the last available assessment. For patients without Visit 32 (Week 57) or Visit 34 (Week 59) assessment, the SFU period would not be derived.

Screen-failure patients (ie, patients screened but not included in the OL Safety Population) and the associated reasons for failure will be tabulated overall for the Screened Population.

The number and percentage of patients in the Screened, OL Safety and OL ITT Populations will be summarized overall and by study center. The number and percentage of patients in the Randomized, DB Safety, and DB ITT Populations will be summarized overall by treatment group and by treatment group and study center.

The number and percentage of patients in the OL Safety Population, who prematurely discontinued from the OLTP, who completed the OLTP, who entered the DBTP, and who entered the SFU period will be summarized overall and by reasons for premature discontinuation as recorded on the OL disposition page of the electronic case report forms (eCRF).

Similarly, the number and percentage of patients in the DB Safety Population who completed the DBTP, who prematurely discontinued from the DBTP, and who entered the SFU period will be summarized overall, by DBTP treatment group and by reasons for premature discontinuation as recorded on the DB disposition page of the eCRF. Patients who relapse during the DBTP will also be summarized as completing the study.

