11.1 ADVERSE EVENTS

Aes will be coded by system organ class and preferred term using the *Medical Dictionary for Regulatory Activities* (MedDRA), Version 21.0 or newer.

An AE will be considered a treatment-emergent adverse event (TEAE) if the AE began or worsened (increased in severity or became serious) on or after the date of the first dose of OL IP. Per eCRF instructions, a new AE record will be created with a new AE onset date for any AE that worsens. Therefore, TEAEs can simply be identified as those Aes with recorded onset date (and time, if known) on or after the date of the first dose of IP.

The number and percentage of patients reporting TEAEs during the OLTP will be tabulated by system organ class and preferred term; by system organ class, preferred term, and severity; and by system organ class, preferred term, and relationship to IP.

The number and percentage of patients reporting TEAEs during the DBTP will be tabulated for each treatment group by system organ class and preferred term; by system organ class, preferred term, and severity; and by system organ class, preferred term, and relationship to IP. The total number and percentage of TEAEs during the DBTP will also be summarized by severity and relationship to IP for each treatment group.

The number and percentage of patients reporting TEAEs during the OL SFU period will be tabulated by system organ class and preferred term for the OL Safety Population. The number and percentage of patients reporting TEAEs during the DB SFU period will be tabulated by system organ class, preferred term, and DB treatment group for the DB Safety Population.

For OLTP, DBTP, or SFU period, if more than 1 AE was coded to the same preferred term for the same patient, the patient will be counted only once for that preferred term using the most severe and most related occurrence for the summarization by severity and by relationship to IP.

An AE that occurs more than 30 days after the date of the last dose of DB IP or occurs after the last SFU visit (whichever comes last) will not be summarized except for Aes related to reported pregnancies. Aes associated with pregnancies reported in the protocol-required timeframe up to approximately 12 weeks following the last dose of DB IP will be summarized.

The number and percentage of patients with common ($\geq 2\%$ of patients in any treatment group) TEAEs will be summarized by preferred term for OLTP and be summarized by preferred term and treatment group for DBTP.

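### Some incompletely dated double-blind adverse events are dated into the open-label period, because SAP 16.7 refers only to the first open-label dose

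*SAP*

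**What the plan says.** SAP 16.7 gives these rules for an AE whose start date is on or after the OL start but incomplete:

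- Month and day missing, year equal to that of the first OL dose: "the month and day of the first dose of OL IP will be assigned to the missing fields".
- Month and day missing, where the known year "is after the year of the first dose of OL IP, *January 1* will be assigned to the missing fields".
- Day missing, month later than that of the first OL dose: "the first day of the month will be assigned to the missing day".
- Start wholly missing, stop date complete: "If the stop date is after the date of the first dose of OL IP", the start becomes the first OL dose date.
- Stop-date check for partial starts: where "the imputed start date as above is after the stop date, the start date will be imputed by the stop date". This can only move a start earlier.

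Three other passages decide what the imputed date does. SAP 7.1 separates the periods: "The DBTP starts with the first day of randomization". SAP 11.1 works from onset date: "TEAEs can simply be identified as those Aes with recorded onset date" on or after the first dose. SAP 11.0 summarises OL safety overall. For the DB treatment period (DBTP), SAP 11.1 says: "The number and percentage of patients reporting TEAEs during the DBTP will be tabulated for each treatment group".

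**The concern.** The trial has two treatment periods, and only the second is randomised. The period in which an AE is counted follows from its onset date, so for an incomplete date the imputation rule chooses the table. SAP 16.7 is written for one question, whether the event began after cariprazine was first taken. It does not address a second question, whether the event began before or after randomisation.

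For any event that began on treatment, each rule picks the first OL dose date, 1 January or the first of the month. Each is at or before the true onset. An OL event can therefore never be pushed into DB, but a DB event can be pushed into OL. At stake is the completeness of the by-arm DB table, which is the only randomised safety comparison in the study. The neighbouring rules lean the other way: SAP 16.5 treats missing severity on treatment as severe, and SAP 16.6 treats missing causality as related.

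**Working it through.** The plan gives no figure on this point to reproduce. The check applies the rules literally to events that truly began in DB.

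**Inputs from the documents.** Randomisation can occur at Day 85, 99 or 113 (Weeks 12, 14 and 16; Protocol Table 1). The DB period lasts 386 − 113 = 273 days = 39 × 7, which agrees with SAP 10.1.

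**Assumptions.** The documents give no AE timing. The first OL dose is taken as equally likely on any day of a 365-day year. DB onset is either uniform over 273 days or front-loaded (exponential, mean 60 days, cut off at 273).

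**Step 1: branch by branch.**

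| Known part of start date | Example | Imputed start | Period |
|---|---|---|---|
| Year only, year of first OL dose | OL 1 Feb 2019, randomised 24 May 2019, AE Sep 2019 | 1 Feb 2019 | moved to OL |
| Year only, later year, randomised in that year after 1 January | OL 1 Oct 2019, randomised 21 Jan 2020, AE May 2020 | 1 Jan 2020 | moved to OL |
| Year only, year after randomisation year | OL 1 Aug 2019, randomised 21 Nov 2019, AE May 2020 | 1 Jan 2020 | stays in DB |
| Day missing, month of randomisation | randomised 24 May 2019, AE 28 May 2019 | 1 May 2019 | moved to OL, unless randomised on the 1st |
| Day missing, later month | AE Sep 2019 | 1 Sep 2019 | stays in DB |
| Start wholly missing, stop after first OL dose | any | first OL dose date | moved to OL |

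**Step 2: share of year-only DB events moved.** The first two rows reduce to one condition: the event falls in the calendar year of randomisation, and randomisation was not on 1 January of a later year than the OL start. With mean onset *m* days after randomisation, the share is 1 − m/365 − 1/365.

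- Uniform onset: m = 136, so 1 − 136/365 − 1/365 = 0.625.
- Front-loaded onset: m ≈ 56.6 after the cut-off, so 1 − 56.6/365 − 1/365 = 0.842. Enumeration on every second day gives 0.843.

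The day of randomisation does not enter the formula, and the enumeration gave the same share for Days 85, 99 and 113. Counting only the first row would give about 36% under uniform onset, so the 1 January branch matters.

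**Step 3: share of DB events missing only the day that move.** These are the events in the rest of the randomisation month. For a month of L days, the mean number of affected days is (L − 1)/2, with zero for randomisation on the 1st. Averaged over the year this is about 14.7 days, and 14.7/273 = 5.4% under uniform onset. Enumeration on every second day gives 5.6%, and 21.8% if onset is front-loaded.

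**Step 4: wholly missing starts.** With a stop date after the first OL dose, 100% of true DB events move, however late the stop date is.

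**Step 5: the reverse direction.** Applying the same rules to true OL onsets moves none of them into DB.

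**The case against.** The strongest reply is that the problem will seldom arise. AEs are asked about at every visit (Protocol 9.1.1). DB visits are two weeks apart, with a final three-week interval (Protocol Table 1). The investigator must supply start and stop dates (Protocol 6.6.1). A DB event known only by its year is therefore improbable; a missing day is the likelier gap, and there most events stay in DB. The OL anchor also serves the definition of treatment-emergent, so nothing is dropped. Serious AEs and AEs leading to discontinuation are listed in any case, and safety is analysed descriptively. All of this stands, and it limits the point to a minor one. It does not supply the missing rule. SAP 4.0 places table specifications in a separate document, which could hold an allocation rule, but neither the protocol nor the SAP states one.

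A reader might infer three stronger things that the documents do not support:

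- That all partly dated DB events move. Step 1 shows two branches that stay in DB.
- That concomitant medication is affected in the same way, because SAP 16.8.1 uses the same start-date rule. SAP 8.0 defines DB concomitant medication by use on or after the first DB dose, not by start. A drug begun in DB still counts in DB when its start is imputed earlier; at most it is also counted in OL.
- That the contrast between arms is biased. The rule is identical in every arm. What is shown is an undercount of DB events and an overcount of OL events, not a differential error.

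**Conclusion.** The point holds in limited form. SAP 16.7 dates a true DB event into OL, and so removes it from the by-arm DB table, in three cases:

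- Only the year is known, and it is either the year of the first OL dose or a later year in which randomisation fell after 1 January.
- Only the day is missing, the month is that of randomisation, and randomisation was not on the 1st.
- The start is wholly missing and the stop date is after the first OL dose.

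The error runs from DB to OL only. The shares in Steps 2 and 3 rest on assumed onset timing and calendar-uniform enrolment. They are shares of an unknown, probably small, number of incomplete dates. No effect on any efficacy result follows. This is a minor correction, worth making because it is cheap and concerns the only randomised safety table.

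**What to change.** Add one clause to SAP 16.7 for randomised patients, before unblinding. It applies when the known date fields, or a wholly missing start, are compatible with both periods. If the AE was first recorded after randomisation and did not stop before the first DB dose, assign the later of the first DB dose date and the earliest compatible date. Otherwise keep the existing rules. SAP 16.8.1 needs no change.

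The recording visit is essential. Simply substituting the first DB dose whenever the known fields match it would remove the DB-to-OL error, but in the same enumeration it moves about 84% to 88% of year-only OL events into DB, and about 13% to 17% of OL events missing only the day. Those events occurred on cariprazine and would be spread over all three arms, placebo included. A stop date alone does not prevent this when the event is ongoing or the stop date is itself incomplete.

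The cost is a few lines of text and programming. The first recording visit must be retrievable from the AE data; the documents do not say whether the form holds it. The remaining downside is that a few OL events first mentioned at the first DB visit may be counted in DB.

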16.8 MISSING DATE INFORMATION FOR PRIOR OR CONCOMITANT MEDICATIONS

For prior or concomitant medications, including rescue medications, incomplete (ie, partly missing) start dates and/or stop dates will be imputed. When the start date and the stop date are both incomplete for a patient, the start date will be imputed first.

16.8.1 Incomplete Start Date

The following rules will be applied to impute the missing numeric fields for an incomplete prior or concomitant medication start date. If the stop date is complete (or imputed) and the imputed start date is after the stop date, the start date will be imputed using the stop date.

Missing month and day

- If the year of the incomplete start date is the same as the year of the first dose of OL IP, the month and day of the first dose of OL IP will be assigned to the missing fields
- If the year of the incomplete start date is before the year of the first dose of OL IP, *December 31* will be assigned to the missing fields
- If the year of the incomplete start date is after the year of the first dose of OL IP, *January 1* will be assigned to the missing fields

Missing month only

- If only the month is missing, the day will be treated as missing and both the month and the day will be replaced according to the above procedure

Missing day only

- If the month and year of the incomplete start date are the same as the month and year of the first dose of OL IP, the day of the first dose of OL IP will be assigned to the missing day
- If either the year of the incomplete start date is before the year of the date of the first dose of OL IP or if both years are the same but the month of the incomplete start date is before the month of the date of the first dose of OL IP, the last day of the month will be assigned to the missing day.
- If either the year of the incomplete start date is after the year of the date of the first dose of OL IP or if both years are the same but the month of the incomplete start date is after the month of the date of the first dose of OL IP, the first day of the month will be assigned to the missing day

16.8.2 Incomplete Stop Date

The following rules will be applied to impute the missing numeric fields for an incomplete prior or concomitant medication stop date for a patient in the respective safety population (OL Safety Population or DB Safety Population). If the date of the last dose of IP in one of the periods is missing, replace it with the last visit date during the corresponding period in the imputations described below. If the imputed stop date is before the start date (imputed or nonimputed start date), the imputed stop date will be equal to the start date.

Missing month and day

- If the year of the incomplete stop date is the same as the year of the last dose of IP, the month and day of the last dose of IP will be assigned to the missing fields
- If the year of the incomplete stop date is before the year of the last dose of IP, *December 31* will be assigned to the missing fields
- If the year of the incomplete stop date is after the year of the last dose of IP, *January 1* will be assigned to the missing fields

Missing month only

- If only the month is missing, the day will be treated as missing and both the month and the day will be replaced according to the above procedure

Missing day only

- If the month and year of the incomplete stop date are the same as the month and year of the last dose of IP, the day of the last dose of IP will be assigned to the missing day
- If either the year of the incomplete stop date is before the year of the date of the last dose of IP or if both years are the same but the month of the incomplete stop date is before the month of the date of the last dose of IP, the last day of the month will be assigned to the missing day
- If either the year of the incomplete stop date is after the year of the date of the last dose of IP or if both years are the same but the month of the incomplete stop date is after the month of the date of the last dose of IP, the first day of the month will be assigned to the missing day

16.9 CHARACTER VALUES OF CLINICAL LABORATORY PARAMETERS

If the reported value of a clinical laboratory parameter cannot be used in a statistical summary table because, for example, a character string is reported for a parameter of the numeric type, a coded value must be appropriately determined for use in the statistical analyses. The actual values, however, as reported in the database will be presented in the data listings.

Table 16.9-1 shows examples of how some possible laboratory results should be coded for the analysis.

Table 16.9-1. Examples of Coding Special Character Values for Clinical Laboratory Parameters

Laboratory Test, SI Unit	Possible Laboratory Results	Coded Value for Analysis
URINALYSIS		
Glucose, mmol/L	= OR > 55, ≥ 55, > 0	Positive
	≤ 0, negative	Negative
pH	> 8.0, ≥ 8.0	8.0
	≥ 8.5	8.5
Protein	= OR > 3.0, ≥ 3.0, > 0	Positive
	≤ 0	Negative

SI = *Le Système International d'Unités* (International System of Units).

17.0 COVID-19 RELATED ANALYSIS

To eliminate immediate potential hazards to patients and study staff due to the COVID-19 pandemic while ensuring participant safety and maintaining data integrity, the protocol clarification letter and corresponding protocol amendment were sent to sites during the pandemic to allow remote visits.

This section specifies analyses for evaluating the impact of COVID-19.

17.1 EFFICACY EVALUATION

For the assessments that are conducted remotely (eg, by telephone, telemedicine virtual visits, and video call) or in-home, the following assessments are required to be completed in the course of the remote visit: YMRS, MADRS, CGI-S, CGI-S, and PSP.

For patients in the OLTP of the study, the following assessments are also required:

- Visits 4 through 7 (as applicable): assessment of remission criteria
- Visit 5 through 8 (as applicable): assessment of stability criteria
- Visit 6 through 12 (as applicable): maintenance of stability
- Visits 10 through 12 (as applicable): assessment of randomization criteria

For patients in the DBTP of the study (Visit 13 through Visit 31/ET), assessment of relapse criteria is also required.

Minimal disruption is expected for the primary endpoint. To evaluate the missing rate for the additional endpoints at the end of OLTP and DBTP, the number of patients who missed the assessments due to COVID-19 will be summarized at each visit in the OL ITT or DB ITT population.

